Study Duration:	November 1, 2021 to April 30, 2024
Participant Duration:	4 to 6 weeks

Primary Objective:	To determine the feasibility, acceptability, and potential efficacy of the culturally competent communication to improve engagement in ACP (i.e., end-of-life discussions with providers and families, completion of advance directives) for Latino patients with advanced cancer.
Secondary Objectives:	Not applicable
Exploratory Objectives:	Not applicable
Endpoints:	
Feasibility will be measured by intervention completion (Benchmark: $\geq 70\%$ complete the intervention sessions).
 
Acceptability will be measured by a single-item question assessing helpfulness of the intervention (1 = not at all helpful, 5 = very helpful) as well an open-ended question about helpfulness of the intervention ("What was helpful about the intervention?") (Benchmark: $\geq 70\%$ rate it as "helpful" or "very helpful").
 
Advance Care Planning Readiness will be measured using the Advance Care Planning Engagement Survey, which is a validated 49-item scale ($\alpha=.94$)¹ designed to assess knowledge, readiness/motivation, and self-efficacy of ACP. Engagement in ACP will measure two key elements of ACP. First, EOL care discussions will be measured by asking patients to self-report whether they have discussed any of the following: (1) wishes they have about the care they would like to receive if they were dying and/or (2) advance care directives, with an oncology provider or family member: DNR orders, living wills, durable powers of attorney for health care, assignments of health care proxies (yes/no format). Second, completion of advance directives will be assessed by examining the medical chart for completed advance directive documents (DNR order, living will, durable power of attorney, health care proxy).

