1.1.2 Hypotheses / Research Questions

The culturally competent communication intervention will be feasible, acceptable, and result in greater engagement in ACP than those in the control condition.

2. Background and Significance

Latino/non-Latino, white disparities are prevalent in ACP and quality of EOL care. Cancer is the leading cause of death among US Latinos.² This highlights the importance of addressing advance care planning (ACP) for Latino cancer patients. So do recent U.S. Census Bureau statistics indicating that Latinos are the fastest growing minority group in the U.S., with expected growth rates of 57% from 2015 to 2050 (totaling to 103 million).³ Latino/white disparities are prevalent in end-of-life care planning and outcomes. For instance, terminally ill Latinos are less likely than non-Latino, whites (hereafter referred to as “whites”) to engage in ACP.⁴⁻⁸ ACP enables patients to achieve their preferred EOL goals of care. Latinos are significantly less likely than whites to engage in two main forms of ACP: (1) end-of-life discussions (32% vs. 85%)⁴ and (2) completing advance directives such as having a living will (9% vs. 67%) or naming a health care proxy (4% vs. 59%).⁴ Engaging in ACP is critical to receiving preferred end-of-life care. Among all groups, patients who engage in ACP have been shown to be significantly more likely to receive care in line with their end-of-life care wishes (86% vs. 30%)⁹ and to die in their preferred place (85% preferred home).¹⁰ The absence of ACP, in turn, is linked to higher rates of death in the Intensive Care Unit (ICU). ICU death is linked to greater physical and emotional distress and poorer quality of life.^{11,12} Latino patients are more likely than their white counterparts to receive aggressive care (e.g., CPR, ICU stays) at the end of life.¹³⁻¹⁵ They are also less likely to use hospice services.^{14,16-18} The aggressive care that Latinos often receive is generally contrary to their preferences and values,¹⁹⁻²⁴ associated with poorer quality of life,^{12,19,25,26} and very costly.¹³

[figure not shown]

Figure 1. Conceptual model of the role of communication competence and social psychological influences on engagement in ACP among Latinos.

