3.4 Exclusion Criteria

Patient exclusion criteria: (1) not fluent in English or Spanish; (2) severely cognitively impaired (as measured by Short Portable Mental Status Questionnaire scores of ≥ 6 to be delivered by trained study research staff during screening);⁴¹ (3) too ill or weak to complete the interviews (as judged by interviewer); (4) currently receiving hospice at the time of enrollment (to allow prediction of ACP); (5) children and young adults under age 18; and (6) patients deemed inappropriate for the study by their treating oncologist. Because the primary outcomes include both completion of advance care planning documentation as well as conversations around ACP, we have chosen not to add exclusion criteria around completion of advance directives. The goal of PLAN is two-fold – which is to increase completion of these documents but also to increase engagement in conversations around ACP with loved ones and providers (which can be present or not present despite completion of documents).

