At UTSW, [name] and other providers within the PHHS palliative care clinic will refer potentially eligible patients to UTSW research study members. A Form HH HIPPA supplement and waiver of authorization has been sent and approved by Fred Hutch and UTSW IRB in order to review EMRs to determine eligibility for recruitment purposes. When an eligible patient is identified and confirmed, the UTSW study member will either approach the eligible patient in person, during a clinic visit, or mail out recruitment material, if they are unable to approach the patient in person. If approaching the eligible patient in person, the study member will coordinate with the clinic staff to find an appropriate time to approach the patient. When approaching the patient, the study member, will proceed to describe the study and give the patient a study flyer. If the research study member is unable to meet the patient during their clinic visit, they will mail the patient an envelope containing a study flyer and information sheet. An information sheet is a UTSW form used to provide study information to potential participants and used for guiding the verbal consenting process. Two weeks after mailing out the letters, UTSW study staff will contact the participant over the phone to gauge interest for study participation. A Form HH Waiver of Consent documentation has been sent and approved by Fred Hutch and UTSW IRB in order to waive documentation of consent (signed form) in order to obtain verbal consent.

If the patient is interested after the in person or telephone call approach, the patient will give verbal consent for participation to the UTSW study member. Once verbal consent has been obtained the UTSW research assistants, will notify the Fred Hutch coordinator. The Fred hutch coordinator and social worker will then carry out the rest of the study procedures with the UTSW participants over the phone. Since the Fred Hutch Coordinator and social worker conduct the remaining study procedures, they will mail out the gift cards to participants who

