3.9 Intervention Administration

A total of 50 Latino advanced cancer patients will be enrolled in this study and randomly assigned to the intervention (n=25) or control (n=25) condition. Pre-intervention, patients'

communication goals will be assessed. Then, patient will participate in the intervention or a usual care control condition. After participating in the intervention or control condition, patients' engagement in ACP will be assessed to determine if the intervention improved ACP engagement and planning.

The intervention itself will be administered by a fully trained, licensed social worker via telephone. This interventionist will use a culturally competent communication intervention to "coach" patients in how to be motivated for and to actually engage in ACP, and will be bilingual in Spanish and English.

Patients randomized into the control group will receive usual care. For usual care, patients will engage in standard care with no modifications. Thus, ACP discussions will only occur as they do in usual clinical care (i.e. brought up in clinical encounters).

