5.1 Schedule of Assessments

Table 1. Schedule of trial events

	Baseline	Post-intervention (with 1 week of completing intervention)	3 mos. after completion of intervention	Off Study
Informed consent	X			
Demographics	X			
Clinical variables				X
Acceptability		X		
Usability		X		
Feasibility		X		
Quality of life	X	X		
Cultural beliefs (Fatalismo, personalismo, respeto)	X	X		
Familial beliefs (Familismo, filial duty)	X	X		
Religious/spiritual beliefs (Religious coping, religious beliefs about end-of-life medical care)	X	X		
Terminal illness acceptance	X	X		
Illness understanding	X	X		
Readiness for ACP	X	X		
Engagement in ACP	X	X		
Healthcare utilization	X	X	X	
Goal-concordant care	X	X	X	

6. Data Reporting / Regulatory Considerations

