as well as satisfaction and helpfulness ratings to determine feasibility and acceptability based on those values being equal to or greater than 70%. We will also conduct qualitative analyses on the open-ended questions related to helpfulness. Thematic analysis using an iterative process will be conducted for all qualitative analyses.⁵⁵⁻⁵⁹ A coding scheme and codebook will be created to analyze transcripts of the responses to the open-ended question. Transcripts will be coded separately by two individual coders for manifest (e.g., frequencies) and latent (e.g., underlying themes) variables. If discrepancies occur, a third coder will resolve these conflicts. Interviews will continue until thematic saturation is achieved.^{60,61} Based on our prior field testing of interventions with patients with advanced illness, we anticipate reaching saturation with n=10 participants. Thus, n=25 in the experimental condition should be well powered to reach thematic saturation.

To examine potential efficacy, preliminary analyses will utilize t-tests to compare the two groups on baseline characteristics (e.g., education, age). Using a criterion of $p < .10$, any variables that are different among the groups will be included in the final logistic regression models as potential confounders. To test the study aim, five separate logistic regression models will be run in which ACP outcomes (yes/no to EOL discussions with family and providers; and the completion of advance directives DNR, health care proxy, and living will) will be predicted by the group variable (CCC intervention vs. control). The statistical power of the proposed logistic regressions to detect a minimum odds ratio of 2.0 for dichotomous outcome measures of ACP, for a two-tailed test with power $(1 - \beta)$ equal to 0.80, and $\alpha = 0.05$, requires a sample size of 113. Our proposed sample size of n=50 will be underpowered if the effect size is small but adequately powered if it is large. However, this study is a preliminary pilot and the main focus and goal of this is to determine feasibility, acceptability, and to provide preliminary data to inform a fully-powered RCT in future research (R01 submission).

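### Baseline discussion status enters the models at best by a p<.10 imbalance rule, so if the item counts any past discussion, the two discussion odds ratios understate PLAN's effect on new discussions

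*Combined protocol and SAP*

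**What the plan says.** The endpoint summary in section 1 and section 3.6 B (Study Instruments) both define the discussion outcome by "asking patients to self-report whether they have discussed any of the following", answered yes or no, with an oncology provider or a family member. Neither gives a start date. The only window in section 3.6 B, from consent to interview, is attached to chart review of directives and palliative care referrals.

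Sections 3.3 and 3.4 do not exclude patients who have already had such discussions. At UT Southwestern, section 3.5 says that "other providers within the PHHS palliative care clinic will refer potentially eligible patients to UTSW research study members", a setting where earlier discussions are plausible.

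Table 1 in section 5.1 schedules "Engagement in ACP" at baseline and post-intervention. Section 7 and the Analytic Plan in section 1 then predict each outcome from study group. They compare arms on baseline characteristics by t-test (education and age are the examples), and at p<.10 "any variables that are different among the groups will be included in the final logistic regression models as potential confounders". Baseline discussion status is not named, and no analysis of new discussions or of change from baseline is given.

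**The concern.** Section 3.4 says that PLAN aims "also to increase engagement in conversations around ACP with loved ones and providers", and section 3.9 says the post-intervention assessment is "to determine if the intervention improved ACP engagement and planning". Those aims concern change during the study. Participation lasts 4 to 6 weeks (section 1), with about four weeks between assessments in the control arm (section 3.8). An item without a start date can count any earlier discussion, which PLAN cannot alter.

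Baseline status on the same item would then be the obvious strong predictor of the outcome. The p<.10 rule selects on chance imbalance, not on prognostic strength, so it would seldom bring that predictor in.

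The stake is mainly in what comes next. Section 7 lists among the pilot's main goals "to provide preliminary data to inform a fully-powered RCT in future research". An odds ratio reported without a window could be read there as the effect on new discussions.

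**Working it through.** **The plan's own figure.** Section 7 states that 113 patients are needed for an odds ratio of 2.0 (80% power, two-sided 5%). For a binary 1:1 group the usual two-proportion formula gives at least 133 per arm (266 in total) over control rates of 4-50%, and 344 in total at 20% v 33.3%. So 113 is not reproduced. That is a separate matter, and nothing below depends on it.

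**Inputs.** From the documents: 25 per arm, two-sided 5%, odds ratio 2.0 (section 7). The share with a prior discussion, b, is not given for this trial. I use 32%, the background figure for Latinos in section 2, and vary it. New-discussion rates p are assumptions: 10% v 40%, 20% v 50%, and 20% v 33.3% (odds ratio 2.0).

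**Dilution.** If every prior yes persists, P(yes) = b + (1-b)p. With o = p/(1-p), the odds of yes are (o+b)/(1-b), so

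OR(ever) = (o1+b)/(o0+b).

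Adding the same b to both terms pulls the ratio toward 1 whenever there is a positive effect. At b = 0.32:
- 10% v 40%: (0.667+0.32)/(0.111+0.32) = 2.29, against 6.0.
- 20% v 50%: (1.00+0.32)/(0.25+0.32) = 2.32, against 4.0.
- 20% v 33.3%: (0.50+0.32)/(0.25+0.32) = 1.44, against 2.0.

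**How often the p<.10 rule acts.** Enumerating all baseline counts at 25 per arm, the t-test gives p<.10 with probability 0.104, 0.101, 0.112 and 0.119 at b = 20%, 32%, 40% and 50%.

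**Power at b = 32%.** The planned and baseline-negative figures are exact enumeration of the two-sided score test. The adjusted figures are simulated Firth models that always include baseline status.

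| New rates | P(yes), ever | Planned | Always adjusted | Baseline-negatives only |
|---|---|---|---|---|
| 10% v 40% | 0.388 v 0.592 | 0.347 | 0.52 | 0.548 |
| 20% v 50% | 0.456 v 0.660 | 0.346 | 0.44 | 0.463 |
| 20% v 33.3% | 0.456 v 0.547 | 0.120 | 0.12 | 0.143 |

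Simulating the p<.10 rule itself gives 0.357 and 0.344 in the first two rows, so it recovers almost nothing.

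**Sensitivity, 10% v 40%.**
- b = 10%: planned OR 3.6, power 0.56; adjusted 0.66.
- b = 20%: planned OR 2.79, power 0.447; adjusted 0.593.
- b = 50%: planned OR 1.91, power 0.213; adjusted 0.392.
- At b = 32%, if 10% or 20% of baseline-positives later answer no, adjusted power is 0.43 or 0.39.

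**If the item is anchored to baseline.** No dilution arises. Across four assumptions about repeat discussions (10% v 40% new), power under the p<.10 rule and with Firth adjustment is 0.733/0.704, 0.651/0.648, 0.388/0.373 and 0.357/0.350. Adjustment then adds nothing.

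**Precision and error rate.** At b = 32% and 10% v 40%, the expected log-OR standard error is 0.58 as planned and 0.95 among the 25 × 0.68 = 17 per arm without a prior discussion. Null rejection is 0.052-0.072 for the planned ever-scored test, 0.022-0.045 with Firth adjustment and 0.033-0.054 in baseline-negatives.

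**The case against.** The strongest reply is that the questionnaire is not in the documents. The protocol only paraphrases the item, and the fielded version may carry a start date. That stands: what is established is an unstated window, and the dilution is conditional on it.

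Second, the power argument depends on large assumed effects. At the protocol's own odds ratio of 2.0, adjustment gives almost no gain. This also stands, although the odds ratio still falls from 2.0 to 1.44.

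Third, the 32% is one background figure, not split by family and provider. With fewer prior discussions the loss is milder.

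Fourth, this is a pilot that already says it is underpowered for small effects, and the hypothesis in section 1.1.2 speaks of greater engagement than control, not of new discussions. That limits the stakes but leaves the odds ratios carried forward to the next trial without a clear meaning.

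Section 7.1 also plans tests of each outcome between arms as a check on randomization. If baseline values are meant, which is unclear, prior discussions would at least be visible by arm. No adjustment would follow.

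A reader might go further and infer confounding or false-positive inflation. Randomization rules out systematic confounding, and persistent prior answers affect both arms alike under the null. Nor does the plan give a wider interval on the log-odds scale; it is narrower than in the restricted analysis. A reader might also extend the point to directives. Section 3.6 B gives chart review a window, so the documents do not support that beyond a wording query.

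**Conclusion.** The point holds in a conditional form. If the discussion item counts any past discussion and prior yes answers persist, the planned odds ratio validly compares ever-discussed status but understates the effect on new discussions, and the p<.10 rule will rarely change that. The direction is algebraic. The size rests on the 32% proxy and the assumed rates.

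The power benefit of routine adjustment is real for large effects, shrinks if prior discussions are rarer or answers do not persist, and is negligible at an odds ratio of 2.0. Adjustment would therefore not make N=50 adequate. Feasibility and acceptability are unaffected. The change is worth making because the baseline data are already scheduled and the estimates are meant to inform the next trial.

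**What to change.** 1. In section 7 and the Analytic Plan in section 1, replace the p<.10 rule for baseline ACP in the two discussion models. Suggested text: *Each discussion model (family, provider) includes baseline status on the same item, whatever the baseline comparison shows. All patients are retained, and an exact stratified or Firth-penalised method is used.* The method matters because persistent yes answers cause separation in ordinary logistic regression.
2. As a supporting result, report first discussions among patients with none at baseline, with the number per arm and a confidence interval, also by an exact or Firth method.
3. State the item's recall window in the section 1 endpoints and section 3.6 B. If the item is already anchored to baseline, say so; item 1 then adds little.

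Cost: no new data are needed for items 1 and 2. The Analytic Plan commits all quantitative analyses to SPSS 23.0, so that statement needs amending if the package does not provide the method. The adjusted odds ratio is conditional on baseline status. The supporting analysis has about 17 per arm at 32% prior discussions, a wider interval and a narrower population. At a 10% control rate its control arm has no events in (0.32 + 0.68 × 0.9)^25 = 17% of trials.

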Analytic Plan:	SPSS version 23.0 will be used to conduct all quantitative statistical analyses. Participants (N=50) will be randomly assigned to the culturally competent communication intervention group or PLAN (n=25) or the control group (n=25). They will then complete measures of engagement in ACP post-intervention. Preliminary analyses will utilize t-tests to compare the two groups on baseline characteristics (e.g., education, age). Using a criterion of $p < .10$, any variables that are different among the groups will be included in the final logistic regression models as potential confounders. Five separate logistic regression models will be run in which ACP outcomes (end-of-life care discussions with family and providers; and the completion of advance directives DNR, health care proxy, and living will) will be predicted by the group variable (intervention vs. control). The statistical power of the proposed logistic regressions to detect a minimum odds ratio of 2.0 for dichotomous outcome measures of ACP, for a two-tailed test with power $(1 - \beta)$ equal to 0.80, and $\alpha = 0.05$, requires a sample size of 113. Our proposed sample size of n=50 will be underpowered if the effect size is small but adequately powered if it is large.

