6.2.5 Record Retention

Essential documents are those documents that individually and collectively permit evaluation of the study and quality of the data produced. After completion of the study, all documents and data relating to the study will be kept in an orderly manner by the Investigator in a secure study file. Essential documents should be retained for 2 years after the final marketing approval in an ICH region or for at least 2 years since the discontinuation of clinical development of the IP. In addition, all subject medical records and other source documentation will be kept for the maximum time permitted by the hospital, institution, or medical practice.

7. Statistical Considerations

Participants (N=50) will be randomly assigned to the intervention group (n=25) or the control group (n=25). They will then complete measures of engagement in ACP post-intervention. Feasibility and acceptability will be examined with frequency and descriptive statistics (i.e., mean, median, standard deviation, range) for enrollment rates, number of sessions completed, number of weeks required to complete the intervention, and Likert-scale items assessing satisfaction with the intervention and perceived helpfulness. Because this is a pilot study, in accordance with published standards for pilot feasibility clinical trials,⁵⁴ inferential statistics on measures of feasibility ($\geq 70\%$ intervention completion rates) and acceptability ($\geq 70\%$ rate it as "helpful" or "very helpful") are not recommended. Rather, we will examine the average rates of completion

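### The directive models have no rule for an arm without events; at a control proxy rate near 4% the odds ratio would have no finite estimate in over a third of trials

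*Combined protocol and SAP*

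**What the plan says.** Section 7 fixes the design: "Participants (N=50) will be randomly assigned to the intervention group (n=25) or the control group (n=25"). For efficacy: "To test the study aim, five separate logistic regression models will be run in which ACP outcomes" (discussions with family, discussions with providers, DNR order, health care proxy, living will) "will be predicted by the group variable (CCC intervention vs. control"). Baseline variables that differ between arms at p < .10 are added. The section names no test statistic and no interval method, and it does not say what happens if an arm has no events. The Analytic Plan in Section 1 adds: "SPSS version 23.0 will be used to conduct all quantitative statistical analyses".

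On power, Section 7 gives a total of 113 patients "to detect a minimum odds ratio of 2.0 for dichotomous outcome measures of ACP" and concludes: "Our proposed sample size of n=50 will be underpowered if the effect size is small but adequately powered if it is large". It states no control-arm rate for any outcome.

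The only Latino directive rates are in Section 2, as literature comparisons of Latino with white respondents: "having a living will (9% vs. 67%) or naming a health care proxy (4% vs. 59". The same passage gives 32% for end-of-life discussions. No Latino rate of DNR completion appears.

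**The concern.** At 4% and 9%, a control arm of 25 expects 25 × 0.04 = 1 proxy event and 25 × 0.09 = 2.25 living wills. Ordinary logistic regression has no finite odds ratio when one arm has no events: the estimate and its standard error grow without limit, and the Wald p-value goes to about 1. A strong effect against an empty control arm would then look like no effect if the Wald output were reported.

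The choice of test is also open. A table of 8/25 against 0/25 gives p near 1 by Wald, 0.0004 by likelihood ratio, 0.0015 by Firth and 0.004 by Fisher. The pilot's stated purpose includes preliminary data for a fully powered trial, so both the estimate and the rule for testing it matter.

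**Working it through.** **Inputs.** 25 per arm, two-sided α = 0.05 (Section 7). Control rates 4%, 9% and 32% (Section 2, background); 15% and 20% are added as assumptions to show the range. No dropout and no covariates.

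**The plan's own figure.** The 113 does not reproduce for a 1:1 binary group variable. With n per arm = [1.96√(2p̄q̄) + 0.842√(p₁q₁ + p₂q₂)]² / (p₂ − p₁)² and an odds ratio of 2.0, a 32% control rate gives p₂ = 0.485 and n = 138, so N = 276. N is 618 at 9% and 1,266 at 4%, and never below 266 on the rates tried. The steps below do not use 113.

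**Step 1: chance of no control events,** (1 − p)²⁵.
- 4%: 0.96²⁵ = 36.0%
- 9%: 0.91²⁵ = 9.5%
- 15%: 0.85²⁵ = 1.7%
- 20%: 0.80²⁵ = 0.4%

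The chance that at least one arm is empty, under no effect, is 1 − (1 − 0.360)² = 59% at 4% and 1 − (1 − 0.0946)² = 18% at 9%.

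**Step 2: Wald ceiling.** An empty control arm cannot be significant by Wald, so power is at most 1 − 0.360 = 64.0% at 4% and 1 − 0.095 = 90.5% at 9%. Exact enumeration of all 26 × 26 outcomes gives maxima of 63.9% (at a PLAN rate of about 70%) and 90.5%.

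**Step 3: power by test, control rate 4%** (same enumeration).

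| PLAN rate | OR | Wald | Likelihood ratio | Firth | Fisher |
|---|---|---|---|---|---|
| 20% | 6.0 | 10% | 49% | 44% | 23% |
| 30% | 10.3 | 35% | 77% | 76% | 61% |
| 40% | 16.0 | 55% | 93% | 92% | 86% |

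At 9% against 40% the contrast narrows: Wald 64%, Fisher 64%, Firth 74%, likelihood ratio 77%.

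**Step 4: true size at nominal 5%.** Likelihood ratio: 5.5% at 4% and 8.5% at 9%. Firth: 1.2% and 4.5%.

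**Step 5: PLAN rate needed for 80% power.**

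| Outcome (assumed control rate) | Wald | Firth | Fisher |
|---|---|---|---|
| Discussions (32%) | about 72% | about 72% | about 73% |
| Living will (9%) | about 48% | about 43% | about 47% |
| Proxy (4%) | not reachable | about 32% | about 37% |

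**Step 6: what Firth returns.** With group as the only predictor, it amounts to adding 0.5 to each cell. For 8/25 against 0/25 the odds ratio is (8.5 × 25.5)/(17.5 × 0.5) = 24.8: imprecise, but finite.

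**The case against.** Five points weigh against the concern.

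- **The test is not specified.** A reader might infer that the proxy model cannot exceed 64% power however large the effect. The documents do not support that. The ceiling belongs to the Wald test, and the likelihood-ratio test of the same model reaches 93% at 4% against 40%. What stands is that the plan leaves the choice open, that the likelihood-ratio test is liberal here, and that no choice of test makes the maximum-likelihood odds ratio finite.
- **The rates are background.** The 4% and 9% are not control-arm assumptions. Section 3.4 does not exclude patients with existing directives, Section 3.3 requires advanced cancer, and Section 3.5 describes palliative-clinic referral at one site. All could raise the rates, and at 15% the problem nearly disappears. This stands, and it makes the point conditional.
- **Section 7.1 plans a two-sample proportions test for each binary outcome.** In its usual pooled form it has 44%, 76% and 93% power at 4% against 20%, 30% and 40%, with size 1.2% at 4% and 4.5% at 9%, so Firth has no power advantage over it. But Section 7.1 presents it as a check that randomization worked, not as the efficacy analysis, and it gives no adjusted estimate.
- **Counts and proportions remain available.** It would therefore be too strong to infer that no usable directive result could reach the next trial. What is lost is the planned odds ratio.
- **This is a pilot.** Feasibility and acceptability do not depend on these models. That lowers the severity but does not remove the gap.

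**Conclusion.** The concern holds in conditional form. If the control proxy rate is near 4%, about 36% of trials would have no control proxy events. The planned odds ratio would then have no finite estimate or usable Wald interval, and a Wald-based test would be limited to about 64% power. The plan has no rule for this case.

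The problem is serious for proxy. It is mild for living will: 9.5% empty control arms, a Wald ceiling of about 90%, and 80% power reachable. A reader might infer that logistic regression also breaks down at 9%, or that the DNR model shares the proxy model's problem. The first is contradicted by the figures, and the second cannot be assessed because no Latino DNR rate is given.

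The power sentence is incomplete rather than false. Whether a large effect is adequately powered depends on the outcome, its control rate and the test, none of which it states.

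These results assume 25 analysed patients per arm and no covariates. Losses would raise the chance of an empty arm; the effect of covariate adjustment was not quantified. Severity: should-fix.

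**What to change.** In Section 7, and in the matching Analytic Plan in Section 1:

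1. For DNR order, health care proxy and living will, replace ordinary logistic regression with Firth penalised-likelihood logistic regression, using a profile-likelihood test and 95% confidence interval.
2. Report beside it the counts per arm, the risk difference with a score-based 95% confidence interval, and Fisher's exact p.
3. Qualify the power sentence by outcome with labelled assumed control rates. At 25 per arm, 80% power needs about 32% against 72% for discussions (Wald or Firth; 73% with Fisher), 9% against 43% (Firth) or 47% (Fisher) for living will, and 4% against 32% (Firth) or 37% (Fisher) for proxy. State that no Latino rate is available for DNR.

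The cost is SAP wording. The Firth fit may need a routine outside standard SPSS, in which case the software statement in Section 1 must change too. No extra patients or data are needed.
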